4.5 Inclusion and Exclusion Criteria

The following inclusion and exclusion criteria are used when determining eligibility patients into the study:

- 4.5.1 Inclusion Criteria
 - Patients suspected of having pulmonary TB
 - Cough ≥ 2 weeks
 - At least one other TB clinical symptom
 - Fever
 - Unexplained weight loss
 - Loss of appetite
 - Hemoptysis
 - Shortness of breath
 - Chest pain
 - Night sweats
 - Fatigue
 - Suggestive TB on chest x-ray based on pulmonologist or internist consultant of pulmonology opinion
 - Age \geq 18 years' old
 - Willing to be treated or evaluated at study site
 - Willing to have specimens stored for use in future studies
 - Patient denies having TB treatment for more than 7 days in the last 1 month (30 days).
- 4.5.2 Exclusion Criteria

Pregnancy or any serious condition includes, but not limited to, liver disease, chronic kidney disease, and psychiatric illness that might interfere with study compliance (based on the clinician judgment). In order to assess participant's pregnancy status, the attending clinician will ask the participant's first day of last menstrual period. The

final decision about participant's pregnancy status will be up to the attending clinician..

- 4.5.3 End of study criteria
 - Study completion (six months after end of treatment or six months after month 24th visit).
 - Participant desires to leave study or withdraw consent.
 - No sputum specimen for the examinations of AFB, Gene Xpert, and culture at baseline and enrollment visit.
 - No longer treated as TB patients.
 - Treatment interruption of two months or greater.
 - Death
 - Transfer to other health facility where follow up/evaluation is no longer possible.
 - Based on investigator's discretion it is in the participant's best interest to be discontinued from the study.
 - Participants who cannot be reached to complete the 6 months' post treatment by phone or direct visit.
 - Termination of study

4.6 Instruments and Data Collection'

The following instruments and data collection methods will be used in this study. Further information may be found in protocol sections 4.6.2-4.6.5.

- 4.6.1 Instruments:
 - a. Forms
 - i. Informed consent
 - ii. Source documents
 - iii. Case report forms (CRFs)
 - iv. Screening Log
 - v. Enrollment Log
 - b. Databases
 - i. OpenClinica

ii. INA-RESPOND specimen database

- c. INA-RESPOND portal
- 4.6.2 Eligibility determination and enrollment:

Enrollment and baseline visit (visit 1)

Potential participants will be referred by physicians at participating hospitals.

Following referral, research assistant will check the eligibility criteria. Thus, the potential participant will be offered information on the study. If the patient agrees, he/she will sign the informed consent document and will be considered enrolled in the study. All baseline procedures should be done in five working days, although the result may come later. Enrollment day is considered as Day 0.

Demography, clinical data, and physical examination results including body weight and height will be obtained. The initial data collection will take time about 30-60 minutes.

Participant should bring enough sputum that can be considered eligible for AFB, Xpert MTB/RIF, and culture examination. Sputum induction by inhalation medicine will be considered for participants that have difficulty to produce sputum according to site SoC. The remaining sputum will be stored for TB related future testing. Participant who cannot provide enough sputum for those examinations will be considered as end of study and stop following the study procedures.

20 cc blood will be drawn for assessment of comorbidities (HIV test and HbA1c), for other examinations needed either for study or for SoC. Such as Hb, ureum, creatinine, AST, and ALT. Left over specimen will be used for future TB related examinations and repository. Less blood volume because unanticipated problem related to blood draw such as collapsing vein would not be considered as protocol deviation. 10 cc of urine will also be collected and stored for future TB related tests. Saliva will also be collected for storage.

After the sputum culture shows positive results of M.*tuberculosis*, the *M.tuberculosis* isolate will be tested for DST and also be stored. New TB cases with Rif susceptible Xpert MTB/RIF result will be tested for first line DST, continue by second line if first line DST result shows drug resistant TB. New TB cases with Rif resistant Xpert MTB/RIF will be directly tested for first and second line DST. Previously treated TB cases will be directly tested for first and second line DST.

DS-TB participants who decide to take the TB treatment in puskesmas (primary health care) may not come to visit(s) except for study visit which the study gives compensation for participant's attendance. So that for those participants, study will provide a record, named "TRIPOD Diary", to be completed on each visit at Puskesmas. The TB program manager or designee at the Puskesmas will give their signed as a verification of this record. TRIPOD Diary will be mentioned further in MOP.

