4.2 Sites and Duration

This study will be conducted at hospitals in the INA-RESPOND network:

- 1. Persahabatan hospital, Jakarta
- 2. [name]. Sulianti Saroso Infectious Diseases hospital, Jakarta
- 3. [name] hospital, Bandung
- 4. [name] hospital, Semarang
- 5. [name] hospital, Surabaya
- 6. Sanglah hospital, Bali

- 7. [name] hospital, Yogyakarta
- 8. [name] hospital, Makassar
- 9. Gatot Subroto Army hospital, Jakarta
- 10. H. Adam Malik Hospital, Medan
- Patients suspected of having pulmonary TB
 - Cough ≥ 2 weeks
 - At least 1 other TB clinical symptoms (fever, unexplained weight loss, loss of appetite, hemoptysis, shortness of breath, chest pain, night sweats, fatigue)
- Suggestive TB on chest x-ray based on pulmonologist or internist consultant of pulmonology opinion
- Age ≥18 years old
- Participants (with or without TB treatment history) are screened whether they meet the following criteria:
 - Willing to be treated or evaluated at study site
 - Willing to have specimens stored for use in future studies
 - Patient denies having TB treatment for maximum 7 days in the last 1 month
 - Pregnancy or any serious condition include, but are not limited to, liver disease, chronic kidney disease, and psychiatric illness, that might interfere with study compliance

[figure not shown]

Figure 1. The Study Plan

The Study will enroll eligible participants for a period of up to 2 years. Participants will be followed up until 6 months' post treatment. For drug susceptible TB, this will be approximately 12 months after enrollment/treatment start, but it may be longer if they have drug resistant TB or require longer treatment regimen for other reasons (e.g. Category 2 treatment, diabetes, etc). For those participants, the study will follow them for maximum 30 months after enrollment/treatment start. Stored specimens will be investigated during the study and/or after study completion.

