- 5) To compare the sensitivity and specificity of AFB and Xpert MTB/RIF relative

to culture result. Sensitivity and specificity will be estimated along with 97.5% confidence intervals. McNemar's statistic will test whether the sensitivity and specificity differ between AFB and Xpert MTB/RIF.

6) To estimate sensitivity and specificity of Rif susceptibility results in Xpert MTB/RIF against result in DST as gold standard along with 97.5% confidence intervals.

More specific plans for these analyses will be developed prior to the start of enrollment, and the plans may be adjusted during the course of the study.

Interim Analyses

Amongst presumptive new TB cases, we estimate that 25% will have confirmed TB, while amongst presumptive previously treated cases, we estimate that 70% will have confirmed TB. In order to ensure adequate numbers of TB cases, the accuracy of these estimates will be evaluated at 6 and 12 months after the study commences. Because of the expected two months waiting period for culture results, earlier looks at the data may not be informative.

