SoC	: Procedure must be done regularly on site

IA : Procedure might be done on site for all or some groups of participants

All available data must be recorded for study

Variables	Measurement	Operational definition
New TB cases	Patient report	TB patients who never have TB treatment or already have TB treatment less than one month (4 weeks)
Previously treated TB cases	Patient report	A patient who has been treated for one month or more with anti TB drugs in the past
Presumptive TB	Clinical and X-Ray evaluation	Patient who presents with symptoms or signs suggestive of TB on the basis of X-ray suggestive TB
Bacteriologically confirmed TB	Laboratory evaluation	A participant whom a biological specimen is positive by AFB or culture or WRD (such as Xpert MTB/RIF)
Clinically diagnosed TB	Clinical and X-Ray evaluation	Participant who does not fulfil the criteria for bacteriological confirmation but has been diagnosed with active TB by a clinician or other medical practitioner who has decided to give the patient a full course of TB treatment, includes cases diagnosed on the basis of X-ray abnormalities
Pulmonary TB	Clinician judgement	Any bacteriologically confirmed or clinically TB involving the lung parenchyma or the tracheobronchial tree, including miliary TB, patient with both pulmonary and extrapulmonary TB should be classified as a case of PTB.
Extrapulmonary TB	Clinician judgement	Any bacteriologically confirmed or clinically diagnosed case of TB involving organs other than the lungs, e.g. pleura, lymph nodes, abdomen, genitourinary tract, skin, joints
Drug Sensitive/susceptible TB	By the result of Drug susceptibility test (DST)	Negative DST result
MDR TB	By the result of Drug susceptibility test (DST)	DST result positive resistant to isoniazid and rifampicin
Rif Resistance TB	By the result of Drug susceptibility test (DST)	DST result positive resistant to rifampicin

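### Baseline sputum may follow TB treatment and no analysis allows for it, so Xpert and AFB specificity against culture can be understated; the effect on the MDR proportion depends on an unstated denominator

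*Combined protocol and SAP*

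**What the plan says.** **Entry.** Section 4.5.1 requires: "Patient denies having TB treatment for more than 7 days in the last 1 month (30 days". Up to 7 days of recent treatment is therefore compatible with entry. The list beside Figure 1 in Section 4.2 words the criterion differently ("Patient denies having TB treatment for maximum 7 days in the last 1 month"), and the two must be reconciled. The operational definitions in Appendix B count as new cases "TB patients who never have TB treatment or already have TB treatment less than one month (4 weeks", so recently treated participants can sit in the new cohort as well as the previously treated one.

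**Sampling.** Section 4.6.2 sets enrollment as Day 0 and states: "All baseline procedures should be done in five working days, although the result may come later". The sputum for AFB, Xpert and culture is one of those procedures. Treatment is given by the patient's own physician (Section 4.3). Section 4.2 treats enrollment and treatment start as one time point ("this will be approximately 12 months after enrollment/treatment start"). No section puts the culture sputum before the first dose.

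**Use of culture.** Secondary objective 5 in Section 4.7.2 takes culture as the only reference for AFB and Xpert: "Sensitivity and specificity will be estimated along with 97.5% confidence intervals". Culture is also the only route to DST. Section 4.6.2 begins that step "After the sputum culture shows positive results of" the organism and says the "isolate will be tested for DST and also be stored". Appendix B defines MDR by DST.

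**Analysis set.** Section 4.4 plans to analyse 250 bacteriologically confirmed participants per cohort, and Appendix B lets a positive AFB, culture or Xpert result confirm a case. Section 4.7.2 gives no denominator for the MDR proportion and does not say how confirmed cases without a DST result are counted. It contains no exclusion, stratum or sensitivity analysis by days of prior treatment.

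**The concern.** Culture depends on live organisms. If treatment before sampling makes some cultures negative while smear or Xpert still detects the organism, the reference standard is wrong for those participants and the index test is blamed. They enter the two-by-two table as false positives, and specificity is understated. The McNemar comparison in objective 5 is exposed too: a lost culture that is Xpert-positive and AFB-negative becomes a discordant pair counted against Xpert. Enrolling more participants does not reduce this bias, and it cannot be measured afterwards unless treatment days before the sputum are recorded.

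The primary objective shares the weakness, because a participant without a culture isolate has no DST result and hence no MDR status. Whether that shifts the MDR proportion, and which way, depends on how such participants are counted.

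**Working it through.** **The plan's own figures (Section 4.4)**
- Enrollment: 250/0.25 = 1,000 new and 250/0.70 = 357 previously treated, total 1,357. This reproduces.
- Exact 95% interval for 30/250 = 12%: (0.0824, 0.1669), matching Table 4.4.1. The running text of Section 4.4 prints the table's n = 300 interval for n = 250; the table row is used here.

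**Inputs derived from the plan**
- Participants not confirmed: 1,000 − 250 = 750 new and 357 − 250 = 107 previously treated, total 857.
- Susceptible (non-MDR) cases at the expected MDR rates: 250 × (1 − 0.019) ≈ 245 new and 250 × (1 − 0.12) = 220 previously treated, total 465.

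**Assumptions (not in the documents)**
- q is the share of susceptible cultures lost to treatment before sampling: (share treated before sputum) × (share of their susceptible cultures turned negative). With 10–40% for each factor, q runs from 0.10 × 0.10 = 1% to 0.40 × 0.40 = 16%; 5% is an intermediate value.
- Every confirmed case would be culture-positive without treatment.
- Xpert stays positive when culture is lost.
- True specificity is 100%.
- No MDR culture is lost, unless stated.

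**Specificity of Xpert against culture**

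Fall = (S × q)/(N + S × q), where S is the number of susceptible cultures and N the number of true negatives.

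| q | Pooled (S = 465, N = 857) | New (S = 245, N = 750) | Previously treated (S = 220, N = 107) |
|---|---|---|---|
| 1% | 4.65/861.65 = 0.5 points | 2.45/752.45 = 0.3 | 2.2/109.2 = 2.0 |
| 5% | 23.25/880.25 = 2.6 points | 12.25/762.25 = 1.6 | 11/118 = 9.3 |
| 16% | 74.4/931.4 = 8.0 points | 39.2/789.2 = 5.0 | 35.2/142.2 = 24.8 |

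If the index test is positive in only a share s of the lost cultures, the fall is multiplied by s. At s = 0.85 the pooled falls are about 0.5, 2.2 and 6.8 points. The same scaling applies to AFB, but the documents give no figure for s. More generally, specificity falls whenever s exceeds 1 minus the true specificity.

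**MDR proportion, previously treated (30 of 250 expected)**
- DST-tested denominator, 30/(250 − 220q): 30/247.8 = 12.1%, 30/239 = 12.6% and 30/214.8 = 14.0% at q = 1%, 5% and 16%.
- Bacteriologically confirmed denominator: a lost susceptible culture that is still Xpert-positive stays in the 250 without being counted as MDR, so the result is 30/250 = 12.0% at every q. If a share g of MDR cultures is also lost, it is 12% × (1 − g): 11.7% at g = 2.5% and 10.8% at g = 10%.

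**MDR proportion, new (1.9% × 250 = 4.75 expected)**
- DST-tested denominator, 4.75/(250 − 245q): 1.9%, 2.0% and 2.3% at the same q. Confirmed denominator: 1.9%.

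**The case against.** The strongest reply is that every number driving the size is assumed. The documents give no share treated before sputum and no rate of culture loss. Appendix B admits cases confirmed by AFB or Xpert alone, so not all 250 per cohort would be culture-positive even untreated. That killed organisms stay detectable, and that susceptible cultures are lost more readily than MDR ones, are premises the documents do not supply. All this stands: the size is unknown, and the table shows a range rather than an estimate.

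Three stronger readings are tempting, and the documents do not support them.

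- **That the MDR proportion is raised.** This needs a DST-tested denominator, which Section 4.7.2 never specifies. On the bacteriologically confirmed set named in Section 4.4, the proportion is unchanged, or falls if MDR cultures are also lost. Even the 14.0% scenario lies inside the interval of 8.2% to 16.7% planned around 12%.
- **That specificity may fall by about 25 points.** That is the worst case among previously treated participants alone. Objective 5 does not split by treatment history, and the pooled worst case is 8.0 points.
- **That sputum is taken after some 14 days of drugs.** This adds 7 permitted days to five working days counted as a full week. The 7 days may fall anywhere in the previous 30, Sections 4.5.3 and 4.6.6 tie the sputum to the baseline or enrollment visit, and the window adds exposure only if drugs are taken before sampling. The plan permits that but does not state it.

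It can also be said that part of the remedy exists. Eligibility already involves asking about recent treatment, Appendix A lists TB history at baseline, and Section 4.7.2 promises more specific analysis plans. None of these commits to recording treatment days before the sputum or to an analysis that uses them.

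**Conclusion.** The point holds for specificity. Followed as written, the plan can score treated, culture-negative TB as a false positive for Xpert or AFB, and it contains nothing to detect or adjust for this. The 7-day allowance in Section 4.5.1 is enough on its own; the baseline window can only add to it. Under the stated assumptions the pooled fall in Xpert specificity is about 0.5 to 8.0 points, with 2.6 points at 5% loss. It would be larger if previously treated participants were reported separately, because only about 107 true negatives are expected there.

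For the primary objective the conclusion is narrower: the MDR proportion can be affected, and its direction cannot be stated until the denominator is. For previously treated cases it moves from 12.0% to between 12.1% and 14.0% if only DST-tested cases count and susceptible cultures alone are lost. With Xpert staying positive, it is unchanged or lower if all confirmed cases count. A low-cost change is justified because the bias has a clear mechanism and its size cannot be recovered later without the treatment-days variable.

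**What to change.** 1. **Section 4.6.2:** collect the sputum for AFB, Xpert and culture as early as possible in the baseline window, without altering when treatment starts. Record in the CRF the number of TB treatment days taken before that sputum. Early collection does not remove treatment already taken before entry, so the recorded variable is the essential part.
2. **Section 4.7.2, objective 5:** report sensitivity and specificity for participants with zero treatment days before sputum alongside the results for all participants.
3. **Section 4.7.2, primary objective:** state the denominator of the MDR proportion and how confirmed cases without a DST result are counted, and report the proportion with and without pre-treated participants.
4. **Sections 4.2 and 4.5.1:** reconcile the two wordings of the 7-day criterion.

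The cost is one CRF field, a sentence on sampling order and additional restricted analyses, with no added test or participant and no change to treatment. The restricted accuracy set is smaller, possibly much smaller if pre-treatment is common: with 10% to 40% treated before sputum (the range assumed above), it would hold about 1,357 × 0.90 = 1,221 down to 1,357 × 0.60 = 814 participants. That is why it should be reported beside the full set and not in place of it.

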4.6.3 Ongoing monitoring and evaluation

During treatment, participants will be seen every month for 6 months and then every 2 months until end of treatment or **maximum at month 24**th. Then participants also will be assessed 6 months after end of treatment. In general, participants will have between 1 to 16 numbers of follow up visits. Study will also record the data of several participants who may need month 7 and/or month 8 and/or month 9 visits, **for example participant receiving category 2 treatment, participant with diabetes comorbid.** Study visits will occur at the same time as clinical visit. If the participant does not come for a clinical visit it will not be considered a deviation from the protocol.

Except 6 months post treatment visit, every study visit will collect data on each comorbidity include HIV, diabetes, and cancer. Study will also collect data on weight, TB symptoms, TB treatment compliance, sputum examination results (if available), and treatment regimen. Participants' compliance will be measured by counting how many medications still left in the blister pack (if available) or based on participant report if the patient does not bring the blister. TRIPOD diary will assist the research assistant to measure participant compliance who is taking the medication in the primary health care/puskesmas.

All participants will have follow up for treatment of TB and routine testing as mandated by the National Guidelines and provided by the hospital in accordance with Appendix A. Additional AFB tests on month 1, culture test on month 1 and 2, and chest x-ray at the end of treatment visit, will be conducted for all drug susceptible participants.

Sputum induction by inhalation medicine will be offered to participants that have difficulty to produce sputum.

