3. OBJECTIVES

3.2 Primary Objective

To estimate the proportion of MDR TB amongst new and previously treated TB cases.

- 3.3 Secondary Objective
 - To evaluate accuracy of clinical diagnosis by comparing clinically defined TB

to laboratory confirmed TB.

- To compare AFB and Xpert MTB/RIF as TB diagnostic tests against culture result.
- To estimate the sensitivity and specificity of Xpert MTB/RIF in detecting Rif susceptibility against Drug Susceptibility Test (DST).
- To estimate the proportion of cured, completed, failed, died and lost to follow up as treatment outcomes in drug susceptible TB (DS-TB) cases and drug resistant TB (DR-TB) cases.
- To evaluate the association of treatment success (cured or completed) with the following data:
 - 1. Demographics (age, sex)
 - 2. TB contact history
 - 3. Smoking habit
 - 4. Treatment seeking behavior
 - 5. Co-morbidities (HIV, DM, cancer)
 - 6. Primary and secondary drug resistance
 - 7. Symptoms
 - 8. Cavitary disease
 - 9. Nutritional status
 - 10. Treatment regimens
 - 11. Patient reported compliance
 - 12. Numbers of bacteria by AFB test
 - 13. TB strains (e.g., Beijing)

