4.7.2 Analysis

This is an observational study to describe rates of MDR TB amongst new and previously treated TB cases in Indonesia. Risk factors for MDR will be evaluated as a secondary objective. Additional secondary objectives include a description of treatment outcomes (cure, failure, death, completed treatment) and evaluation of associated risk factors for poor outcome, comparison of diagnostic accuracy of AFB and Xpert MTB/RIF (relative to culture) and an estimation of Xpert MTB/RIF Rif susceptibility testing sensitivity and specificity relative to standard DST. Research objectives will be analyzed as described below.

Primary objective

 To estimate the rate of MDR-TB amongst new and retreated TB cases. Proportions of MDR will be estimated, along with exact 95% confidence intervals based on a binomial distribution. Case definitions of MDR, new and previously treated TB are provided in Appendix B.

Secondary objective

- To estimate treatment outcomes (cured, failed, died, treatment completion, and lost to follow up) according to susceptibility pattern. Proportions of participants within each category will be estimated along with confidence intervals. Definitions of treatment outcomes are provided in appendix B.
- 2) To evaluate risk/protective factors for treatment success (cured or completed treatment vs failed or died or loss to follow up). These factors include: demographics (age, sex), TB contact history, smoking habit, treatment seeking behavior, co-morbidities (HIV, DM), primary drug resistance, symptoms, no cavity in the lung, nutritional status, treatment regimens, compliance, numbers of bacteria and TB strains (e.g., Beijing). Logistic regression models will be used to describe associations of treatment success with these factors.
- 3) To evaluate risk/protective factors for treatment interruption (loss to follow up vs other treatment outcome). These factors include: demographics (age, sex), TB contact history, smoking habit, treatment seeking behavior, co-morbidities (HIV, DM, and other comorbidities), primary drug resistance, symptoms, cavity in the lung, nutritional status, treatment regimens, compliance, numbers of bacteria and TB strains (e.g., Beijing). Logistic regression models will be used to evaluate associations of treatment interruption with these risk factors.
- To compare clinically defined TB against laboratory confirmed TB. Accuracy will be estimated along with 97.5% confidence intervals.

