Failed	Attending TB team report	 Treatment terminated or need for permanent regimen change at least two anti-TB drugs because of: Lack of conversion at the end of intensive phase; or Bacteriologocial reversion in the continuation phase after conversion to negative; or Evidence of additional acquired resistance to fluoroquinolones or second-line injectable drugs; or Adverse drug reactions
Died	Attending TB team report	Died for any reason during course of treatment
Loss to follow up	Attending TB team report	Treatment was interrupted for two consecutive months or more.
Not evaluated	Attending TB team report	No treatment outcome is assigned. This include cases 'transferred out' to another treatment unit as well as cases for whom the treatment outcome is unknown.
Treatment success	Attending TB team report	The sum of Cured and completed treatment.

Demographics						
Age	Patient report	Last birthday				
Sex	Patient report	male and female				
Patient's history						
TB close contact	Patient report	Living in a same house with person who has TB				
Smoking habit	Patient report	Smoking status of participants				
Treatment seeking behavior	Patient report	History of health facility that been visited for treating these TB symptoms				
Co Morbidities						
HIV	Clinical and laboratory evaluation support HIV evidence	Positive result of HIV test				
Diabetes mellitus	Clinical and laboratory evaluation support diabetes evidence glucose test according to site SoC	Positive result of diabetes				
Symptoms	Patient report	Presence of TB symptoms from previous visit to current visit				
Nutritional status	BMI calculation based on data of Height and weight	< 18.5				
Treatment regiment	Source documents	Regiment of anti TB drugs given to the patients according to SoC				
Compliance	Patient report or blister count	Percentage of scheduled medication minus any medication left in the blister or based on patient report				

REFERENCES

1. World Health Organization W. Global Tuberculosis Control, Surveillance, Planning and Financing. Geneve: 2006.

2. World Health Organization W. Global Tuberculosis Control 2010. Geneve: 2010.

3. World Health Organization W. Global Tuberculosis Report 2016. Geneva: World Health Organization; 2016.

4. Departemen Kesehatan Republik Indonesia. Pedoman Nasional Penanggulangan Tuberkulosis. Jakarta2007.

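### Compliance merges blister counts and self-report, chosen by whether the blister is brought; with no record of source, this could bias its odds ratio in two secondary models

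*Combined protocol and SAP*

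**What the plan says.** Section 3.3 item 11 lists "Patient reported compliance" among the factors to be related to treatment success. Section 4.6.3 describes a different measure: "counting how many medications still left in the blister pack (if available) or based on participant report if the patient does not bring the blister". Appendix B follows 4.6.3 and defines a single variable: "Percentage of scheduled medication minus any medication left in the blister or based on patient report".

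A third source exists for some participants. Section 4.6.3 states that "TRIPOD diary will assist the research assistant to measure participant compliance who is taking the medication in the primary health care/puskesmas". Section 4.6.2 limits this diary to DS-TB participants treated in primary care, provides that "The TB program manager or designee at the Puskesmas will give their signed as a verification of this record", and leaves further detail to the manual of procedures, which is not among the documents.

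Section 4.7.2 lists compliance as a factor in both association analyses. For item 2, "Logistic regression models will be used to describe associations of treatment success with these factors". For item 3, "Logistic regression models will be used to evaluate associations of treatment interruption with these risk factors". The documents set no priority for the diary against the other two sources, do not say that the source is recorded, and plan no term, stratum or sensitivity analysis by source.

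**The concern.** The participant's own behaviour decides which instrument is used. If self-report misses more non-compliance than a count does, and participants heading for a poor outcome bring the blister less often than equally compliant participants who do well, non-compliance is under-recorded more in the unsuccessful group. That is measurement error that differs by outcome. Unlike ordinary misclassification, it can move an odds ratio away from 1 when there is no true effect, and it can hide a modest real effect.

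The link to outcome is not far-fetched. Loss to follow-up counts as non-success in item 2 and is the outcome in item 3, and Appendix B defines it largely by interruption of treatment. Outcome and bringing the blister are therefore both partly matters of engagement with care. At stake is how one factor is interpreted in two secondary analyses. With the source unrecorded, an analyst could not tell afterwards whether switching of instrument had shaped the result.

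**Working it through.** The plan gives no figure for this point, so there is none to reproduce. What can be checked is whether the mechanism works, and under which conditions.

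**Inputs, all assumed.** Compliance is reduced to compliant or non-compliant for simplicity. True non-compliance is 20% in both outcome groups (no effect). Count: sensitivity 0.95, specificity 0.95 for non-compliance. Self-report: sensitivity 0.40, specificity 0.97. Let b be the proportion of an outcome group that brings the blister.

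**Formulas.** Sensitivity = 0.95b + 0.40(1 − b). Specificity = 0.95b + 0.97(1 − b). Recorded non-compliance = 0.20 × sensitivity + 0.80 × (1 − specificity). The odds ratio compares recorded non-compliance in unsuccessful with successful participants.

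**No true effect, bringing differs by outcome.** For b = 0.40: sensitivity 0.620, specificity 0.962, recorded 0.1240 + 0.0304 = 0.1544. For b = 0.70: sensitivity 0.785, specificity 0.956, recorded 0.1570 + 0.0352 = 0.1922. Odds ratio = (0.1544/0.8456)/(0.1922/0.8078) = 0.77.

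| Bring blister: unsuccessful vs successful | Recorded non-compliance | Odds ratio |
|---|---|---|
| 60% vs 60% | 0.1796 vs 0.1796 | 1.00 |
| 50% vs 60% | 0.1670 vs 0.1796 | 0.92 |
| 40% vs 70% | 0.1544 vs 0.1922 | 0.77 |
| 20% vs 70% | 0.1292 vs 0.1922 | 0.62 |

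At 40% vs 70%, self-report sensitivities of 0.30, 0.60, 0.70 and 0.80 give 0.73, 0.85, 0.88 and 0.92. The bias shrinks as self-report improves.

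**No true effect, bringing depends only on true compliance.** Let 70% of compliers and 40% of non-compliers bring the blister, whatever their outcome. Recorded non-compliance = 0.20 × (0.40 × 0.95 + 0.60 × 0.40) + 0.80 × (0.70 × 0.05 + 0.30 × 0.03) = 0.1240 + 0.0352 = 0.1592 in both groups. The odds ratio is 1.00. So the link with outcome must exist at the same true compliance.

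**A true effect.** Take non-compliance of 0.40 in unsuccessful and 0.10 in successful participants: (0.40/0.60)/(0.10/0.90) = 6.0. Self-report in everyone records 0.40 × 0.40 + 0.60 × 0.03 = 0.178 and 0.10 × 0.40 + 0.90 × 0.03 = 0.067, an odds ratio of 3.02. The merged measure gives 3.73 (60% vs 60% bringing), 3.47 (60% vs 70%), 3.11 (50% vs 70%) and 2.77 (40% vs 70%). With bringing driven only by compliance it gives 3.34.

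For a modest true odds ratio of 1.5 (20% non-compliance among successes, 27.3% among non-successes) at 40% vs 70%, the merged measure gives 1.03 and uniform self-report 1.30.

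**A second set of assumptions.** Good compliance is 70%, the count is error-free, and self-report identifies a proportion s of poor compliers. Recorded good compliance = 0.70 + 0.30(1 − b)(1 − s). With no true effect, 80% of successes and 40% of non-successes bringing, and s = 0.3, 0.5 or 0.7, the odds ratio for good compliance is 0.61, 0.72 or 0.83. At 70% vs 50% it is 0.78, 0.85 or 0.91. The direction is the same.

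**The case against.** The strongest objection is that the natural mechanism is for poor compliers to leave the blister at home. Bringing then depends on true compliance alone, and the null odds ratio stays at 1.00. This stands. The bias needs the narrower condition that outcome groups differ in bringing at equal compliance, and the documents offer no evidence of it. General disengagement from care is a conceivable route, no more. The larger figures also rest on wide gaps in bringing and a wide gap in accuracy; at 50% vs 60% the odds ratio is 0.92.

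A reader might infer that poor outcome will look like good compliance. The documents do not support that. A reversal needs compliance to have little or no effect on outcome, which is hard to credit when loss to follow-up is itself largely interrupted treatment. With a true odds ratio of 6.0 the merged measure still gives 2.77 at 40% vs 70%.

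A reader might also infer that the remedy is to make self-report the sole compliance variable, since item 11 names it. That is a trade-off. At a true odds ratio of 6.0, uniform self-report (3.02) is further from the truth than the merged measure in every case shown above except 40% vs 70%. Self-report error can itself differ by outcome: with sensitivity 0.30 in unsuccessful and 0.50 in successful participants, recorded non-compliance is 0.084 vs 0.124 and the null odds ratio is 0.65.

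Nor does the text say that the diary is merged into the percentage. It assists the measurement, and Appendix B does not mention it. The CRF and manual are not supplied, and 4.7.2 defers detailed analysis plans, so the source may be captured somewhere not shown.

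What survives is that the definitions disagree, and that no stated provision would let the study detect an effect of switching instrument.

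**Conclusion.** The point holds as a cheap improvement to secondary analyses. Merging two instruments, chosen by the participant's behaviour, can bias the compliance odds ratio in items 2 and 3 of section 4.7.2. Under the first set of assumed accuracies, with no true effect, the odds ratio runs from 0.92 to 0.62 as the gap in bringing widens from 50% vs 60% to 20% vs 70%. It is 1.00 if bringing is unrelated to outcome or depends only on true compliance.

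Whether the bias will occur in this study cannot be said, because every rate used is an assumption. Compliance is one of 13 listed factors, and the primary estimate of the MDR proportion does not use it. The mismatch between item 11 and the measure in 4.6.3 and Appendix B needs no assumption: it is plain on the page.

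**What to change.** - At every treatment visit, ask every participant the same self-report question, whether or not the blister is brought.
- Record on the CRF the source of each compliance value: count, report or diary.
- Reconcile section 3.3 item 11, section 4.6.3 and Appendix B so that they describe the same measure or measures, and state how diary information is used.
- In items 2 and 3 of section 4.7.2, report the compliance association for uniform self-report and for counts among those who have a count, alongside any combined measure. Do not rely on the merged variable alone.

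The cost is one question and one source field at existing visits, some wording, and a sensitivity analysis. Section 4.7.2 already allows its analysis plans to be adjusted during the study. If enrolment has begun, source can be recovered for past visits only where source documents show it. Self-report is the coarser measure, and the subset with counts is itself selected by who brings the blister, so neither result should be presented as free of bias. Their agreement or disagreement is the useful information.
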